## **10.6 12-lead ECG**

### **10.6.1 Definition of variables**

- Heart Rate (beats/min)
- PR interval (msec)
- QRS interval (msec)
- QT interval (msec)
- QTcF interval (msec)
- Overall interpretation of 12-lead ECG:
  - Normal
  - Abnormal NCS (Not Clinically Significant)
  - Abnormal CS (Clinically Significant).

### **10.6.2 Biostatistical methods**

Descriptive statistics will be calculated for heart rate, PR interval, QRS interval, QT interval, and QTcF interval, including change from baseline (last pre-dose value on Day 1) for each dose level (cohort) for all time points assessed.

12-lead ECG measurements will be obtained at the scheduled time points after the participant is semi-supine for at least 3 minutes. Any abnormal ECGs will be repeated in triplicate, with each measurement approximately 1 minute apart. If triplicate ECG parameters are available, the average of the triplicate ECG parameters will be used. Unscheduled visits will be excluded from summary tables. However, the findings from the unscheduled will be listed.

In addition, the overall interpretation of 12-lead ECG results will be classified using frequency counts and percentages for the categories of Normal, Abnormal - Not Clinically Significant (NCS) and Abnormal - Clinically Significant (CS) for each treatment group for all time points assessed.

All ECG data will be presented in the by-subject data listings.

## 11. VIROLOGY

Virology endpoints are only collected for CHB cohorts across the study period according to the protocol schedule of assessment. The analysis population for virology data is PD.

Virology endpoints will be analyzed separately for the main study (up to Day 113 EOS) and for the overall study duration, including the follow-up period, for the subset of patients that consented to participate in the follow-up. Endpoints will be derived separately for each analysis taking into consideration all the applicable data for the specific period.

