11.6 Pharmacodynamic Data

The whole blood collected for pharmacodynamic analysis following multiple doses of ARO-HBV at different dose levels will undergo analysis for changes in HBV-DNA, HBV-RNA (if scientifically feasible) and viral antigens based on reference laboratory (VIDRL) generated values. Cellular immunologic assessments will also be conducted (if scientifically feasible) at University of Auckland.

Immunology assessments (CHB patients in New Zealand only)

- Changes in profile from pre-dose to post-dose time points for: T cell subsets (activation and exhaustion state), NK cell subsets (activation and exhaustion state), B cell subset, monocyte subsets. To be conducted if scientifically feasible.
- Changes from pre-dose to post-dose time points for: HBV antigen specific T cell response (including HBcAg, HBsAg). To be conducted if scientifically feasible.

Virology assessments (CHB patients only)

- Virologic parameters will be summarized by cohort for the following:
- Quantitative HBsAg (qHBsAg): Log change from baseline to nadir and duration of response from nadir back to approximately 20% of baseline or EOS. In CHB patients who consent to additional follow up, HBsAg will be followed until the end of the additional follow-up period or early termination and summarized separately.
- Percent of patients with loss of HBsAg (defined as quantitative HBsAg < 0.05 IU/mL) at EOS and time to occurrence (Kaplan Meier). In CHB patients who consent to additional follow up,

HBsAg loss will be monitored until the end of the additional follow-up period or early termination and summarized separately.

- Percent of patients with anti-HBS seroconversion at EOS and time to occurrence (Kaplan Meier). In CHB patients who consent to additional follow up, anti-HBS seroconversion will be monitored until the end of the additional follow-up period or early termination and summarized separately.
- Change in Anti-HBs (quantitative) to EOS. In CHB patients who consent to additional follow up, change in Anti-HBs (quantitative) will be monitored until the end of the additional follow-up period or early termination and summarized separately.
- Quantitative HBV DNA (when quantifiable at baseline): Log change from baseline to EOS. In CHB patients who consent to additional follow up, HBV DNA will be monitored until the end of the additional follow-up period or early termination and summarized separately.

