### 3. STATISTICAL CONSIDERATIONS

Data will be handled and processed according to the sponsor's representative (Novotech (Australia) Pty Ltd) Standard Operating Procedures (SOPs), which are written based on the principles of GCP.

All data collected on the eCRFs will be presented in the data listings and will be listed and sorted by subject number and visit, where applicable. All summaries will present the data by ARO-HBV dose level/cohort and overall (total subjects), as applicable.

Data collected during the main study (up to the Day 29 or Day 113 EOS visits) and at the additional follow-up visits (CHB cohorts only) will be presented in the same summary table, as appropriate. The first part of each table will present the main study results for the specific analysis. The second part of each table will include all data collected during the study, including data collected during the follow-up period, for the subset of CHB patients that consented to participate in the follow-up. All data will be included in the listings, and data collected during the follow-up period will be flagged in all event/medication-based listings. Separate figures that include all data will be presented for the subset of patients that participated in the follow-up period.

Unless otherwise stated, the following statistical approaches will be taken:

- Continuous variables: Descriptive statistics will include the number of non-missing values (N), mean, standard deviation (SD), median, minimum, maximum.
- Categorical variables: Descriptive statistics will include frequency counts and percentages per category. Percentages will be rounded to one decimal place, with the denominator being the number of subjects in the relevant population with non-missing data, unless otherwise specified.
- Imputation: No missing data will be imputed generally.
- Confidence intervals (CIs): CIs will be two-sided and will use 95% confidence levels unless specified otherwise.
- Baseline: Baseline values will be defined as the last non-missing observation (pre-dose value closest to the first dose) for each subject prior to the dosing of study medication (i.e. start of injection on Day 1).
- Repeat assessments (Safety): If there is a repeat test, the repeat result will be used in the analysis table and the original result will only be listed in the data listing.

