### Time to Event Endpoints

- Time to HBsAg Loss is defined as the duration from first dosing to the date of HBsAg 'Not Detected' (HBsAg loss defined as HBsAg < 0.05 IU/mL). Subjects without HBsAg loss will be censored at the end of study (or the end of follow-up period).
- Time to anti-HBsAg seroconversion is defined as the duration from first dosing to the date of anti-HBsAg seroconversion. Subjects without anti-HBsAg seroconversion will be censored at the end of study (or the end of follow-up period).
- Duration of Response (for HBV DNA, qHBsAg, qHBeAg, qHBcrAg, qHBV RNA): defined as the duration from post dose nadir back to within 20% of baseline value. The analysis will only be performed for the overall study period (including the follow-up period) and only patients with baseline values above the LLQ for the specific parameter will be included in the analysis. Subjects with the endpoint not returning to within 20% of baseline value will be censored at the end of the follow-up period.

The time to event endpoints will be analyzed by survival analysis method. Survival analysis will only be conducted if there are at least some responders within a cohort. The survival functions of the time to event endpoints will be summarized for 25th percentile, median, and 75th percentile and their 95% confidence intervals. The rates of HBsAg Loss and anti-HBsAg seroconversion at Day 60 and Day 113 post dosing (and also at Days 169, 225, 281, 337 and 393 for the subset of CHB subjects that participated in the follow-up), the response rates (for HBV DNA, qHBsAg, qHBeAg, qHBcrAg, qHBV RNA) at Day 30 and Day 60 (and additional time points at 30 days intervals as appropriate) post nadir, and their respective 95% confidence intervals will be derived based on their survival functions estimated by Kaplan-Meier method. In addition, the graphs of Kaplan-Meier estimates of survival functions (survival plots) will be presented. Histograms will also be presented showing the response rates for each cohort over 30-day intervals.

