### **17.3 Final Analysis (End of Study)**

The final end of study analysis will be based on the final version of the SAP. If feasible, Clinical Study Report analysis of quantitative HBsAg through EOS (Day 113) and Additional Follow-Up (Day 393) will be based on a final batched analysis of samples. PD analyses will be completed at EOS (Day 113) and at the end of additional follow up period only in subjects entering into the additional follow up period.

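### Duration of response is confined to patients who consented to follow-up, so a rebound by Day 113 in a patient who does not continue is counted in no estimate

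*SAP*

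**What the plan says.** SAP section 11 (Virology) sets up two analyses: the main study to Day 113, and a second one "for the overall study duration, including the follow-up period, for the subset of patients that consented to participate in the follow-up". SAP section 3 repeats the restriction for the second part of each summary table, which holds all data "for the subset of CHB patients that consented to participate in the follow-up". SAP 17.3 repeats it for the final PD analyses, which are done at Day 113 and "at the end of additional follow up period only in subjects entering into the additional follow up period".

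Under Time to Event Endpoints, DoR is "defined as the duration from post dose nadir back to within 20% of baseline value". It is assigned to one period only ("The analysis will only be performed for the overall study period (including the follow-up period"). The single censoring rule is: "Subjects with the endpoint not returning to within 20% of baseline value will be censored at the end of the follow-up period".

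The protocol is wider. Section 11.6, like the synopsis, specifies for quantitative HBsAg: "Log change from baseline to nadir and duration of response from nadir back to approximately 20% of baseline or EOS". For patients who continue, it then adds that "HBsAg will be followed until the end of the additional follow-up period or early termination and summarized separately". Protocol 6.4 treats a CHB patient as having completed the study at Day 113, with later visits depending on re-consent.

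**The concern.** Read together, these rules let a later choice decide who enters an analysis whose clock has already started. DoR runs from nadir. A patient can reach nadir, rebound and finish the study at Day 113 with the whole event on record, and still be left out for declining further visits. The protocol does not say when re-consent is signed, but the follow-up visits come after Day 113, and the clock for any rebound seen by Day 113 started earlier.

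At stake is the plan's only estimate of how long viral suppression lasts. Protocol 4.6 argues that a longer period of low antigen is more likely to be beneficial, and SAP 2.4 says the results will be used in sample-size calculations for later studies. If the decision to continue is related to having lost response, the reported durability describes a selected group.

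**Working it through.** **Pool of patients.** SAP 2.4 gives 60 to 84 CHB patients. From its cohort sizes (six cohorts of 4 to 8, six of at most 4, and Cohort 12 with 12):
- minimum 6×4 + 6×4 + 12 = 60
- maximum 6×8 + 6×4 + 12 = 84

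Both reproduce. Neither document gives the share expected to enter follow-up.

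**Which patients reach DoR.**

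| Rule | Place | Consequence |
|---|---|---|
| DoR only for the overall period | SAP 11, Time to Event Endpoints | No Day 113 version |
| Overall period limited to consenters | SAP 11; also SAP 3 and 17.3 | Non-consenters are out |
| Censoring only at end of follow-up | SAP 11, Time to Event Endpoints | No rule for data ending at Day 113 |
| All DoR plots and histograms titled as follow-up outputs | SAP 21, figures 14.2.8.3 to 14.2.8.12 | Agrees with this reading |
| HBsAg DoR to rebound or EOS | Protocol synopsis and 11.6 | A non-continuing patient counts |

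The censoring rules for HBsAg loss and seroconversion offer end of study or end of follow-up. The DoR rule offers only the latter.

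**Whether a rebound by Day 113 can be observed.** From last dose to Day 113:
- Q28D: 113 − 57 = 56 days
- Q14D: 113 − 29 = 84 days
- Q7D: 113 − 15 = 98 days

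Protocol Table 1.2 has quantitative virology at Days 71, 85 and 113. A nadir at Day 85 with return at Day 113 is a 28-day event (113 − 85); a nadir at Day 71 gives 42 days (113 − 71). Both are complete DoR events, and they fall before the SAP's Day 30 and Day 60 post-nadir landmarks respectively.

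**Size of one omission (illustrative counts).** Suppose rebounders return at 28 days and do not continue, and everyone else continues without rebound. The Day 30 Kaplan-Meier response rate is then:

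| Cohort | Omitted rebounds | All patients | Consenters only |
|---|---|---|---|
| 4 | 1 | 3/4 = 75% | 3/3 = 100% |
| 8 | 1 | 7/8 = 87.5% | 7/7 = 100% |
| 8 | 2 | 6/8 = 75% | 6/6 = 100% |

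Now let two of the six non-rebounders in the last row also stop, censored at 42 days. The all-patient estimate stays at 75% at Day 30 and Day 60, and the consenter-only estimate is 4/4 = 100%.

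**Direction.** Let p be the share rebounding by Day 113, and cN and cR the consent rates in non-rebounders and rebounders. The expected response rate among consenters is (1−p)cN / [(1−p)cN + p·cR]. With p = 25% (true rate 75%), and consent rates that are assumptions:

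| cN | cR | Calculation | Consenter-only rate |
|---|---|---|---|
| 80% | 80% | 0.60/(0.60+0.20) | 75.0% |
| 80% | 50% | 0.60/(0.60+0.125) | 82.8% |
| 80% | 20% | 0.60/(0.60+0.05) | 92.3% |
| 80% | 0% | 0.60/0.60 | 100% |
| 50% | 80% | 0.375/(0.375+0.20) | 65.2% |

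The bias can be nil, upward or downward.

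**How many rebounds there would be.** This depends on the threshold. On the raw scale, the SAP's event is a return to at least 80% of baseline (log10 0.8 = −0.10). The protocol's wording, read literally, is a return to about 20% of baseline (log10 0.2 = −0.70), which would be met earlier. Under the SAP threshold fewer rebounds would fall before Day 113.

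**The case against.** The strongest reply is that the exclusion is inferred. The SAP's own DoR inclusion sentence names only a baseline above the LLQ, and overall study period could describe a span of time and not a set of patients. SAP section 19 marks DoR tables 14.2.4.6 to 14.2.4.10 for the Day 113 interim and says tables are produced for the CHB cohorts as well as the follow-up subset. SAP section 20 lists time-to-event endpoints with and without a follow-up label. This shows the text is not uniform. It does not settle the matter, because the interim mark also stands against the DoR figures that are explicitly titled as follow-up outputs.

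A second reply concerns the time origin. Non-consenters' nadir is cut off at Day 113, while consenters' nadir may fall later. That is a real limitation of pooling them, but it does not defeat inclusion: a patient still declining at the last visit is censored at time zero and adds nothing.

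Third, little is hidden. By-visit changes and plots to Day 113 cover all PD patients with baseline above the LLQ, all virology data are listed, and the number entering follow-up is tabulated. The study is descriptive, DoR is in no primary or secondary objective, and Cohort 12 follow-up is worded as required to Day 337. This limits the importance of the point.

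A reader might infer that HBsAg loss and seroconversion suffer equally. The documents do not support that. Both keep Kaplan-Meier rates at Day 60 and Day 113 in the main-study analysis, and Protocol 11.1 and 11.6 themselves ask for a separate follow-up summary. The later rates can differ somewhat. With 5 of 8 consenting, and losses among consenters at Days 113 and 281, the Day 393 rate is 1 − (4/5)(3/4) = 40% in consenters, against 1 − (7/8)(3/4) = 34.4% with non-consenters censored at Day 113. That gap exists only because one loss falls by Day 113, where the full analysis already counts it.

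**Conclusion.** The point holds for DoR. On the wording of SAP sections 3, 11 and 17.3 and the figure titles, a non-consenting patient who rebounds by Day 113 is excluded from every DoR estimate, contrary to the protocol's HBsAg definition. One such omission can move a rate by about 12.5 points in a cohort of 8 and 25 in a cohort of 4, assuming the remaining patients continue without rebound.

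Two further inferences are not supported. One is that durability will be overstated: non-consenters who kept their response are dropped too, and no consent rates are given, so direction and overall size are unknown. The other is that Kaplan-Meier censoring would remove the selection. It recovers events seen by Day 113; if stopping is related to response, censoring at that point remains informative.

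**What to change.** In SAP section 11, Time to Event Endpoints:
- Include in DoR all PD-Population patients with baseline above the LLQ for the parameter, whether or not they entered follow-up.
- Count every rebound observed up to the patient's last assessment.
- Censor patients without rebound at their last available virology assessment (Day 113 or earlier for those not entering follow-up), not only at the end of the follow-up period.
- Keep the consenter-only DoR as a supplementary analysis.
- Align the DoR tables in section 19 and the figure titles in section 21.
- State as limitations that non-consenters' nadir is observed only to Day 113, and that censoring there may be informative.

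The cost is SAP wording and a rerun of the DoR outputs. No new data are needed.

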### Data Handling Rules

The units and lower limit of quantitation (LLQ) cut-off and imputed values in the table below will be used in all derivations and outputs.

Parameter	Qualitative / Quantitative	LLQ	Unit	Values for Imputation		
				< LLQ	< LLQ Detected	< LLQ Not Detected
HBeAg	Qualitative	0.22	PEIU/mL	N/A	N/A	N/A
qHBeAg	Quantitative	0.11	PEIU/mL	0.055	0.055	0.055 a)
HBV DNA	Quantitative	20	IU/mL	N/A	15	5
HBV RNA	Quantitative	1.65	Log10 U/mL	N/A	0.825	0.4125
qHBcrAg	Quantitative	1	kU/mL	0.5	N/A	N/A
qHBsAg	Quantitative	0.05	IU/mL	0.025	N/A	N/A

a) Values below 0.11 PEIU/mL may have been reported as 'not detected'

All reported qHBsAg and qHBcrAg results below the LLQ cut-off values will be treated as below LLQ and included in the '< LLQ' category counts.

qHBeAg results will be imputed based on the reported HBeAg (qualitative) results provided by the analyzing laboratory:

- Positive: All reported qHBeAg results equal to or above the LLQ cut-off value (0.11 PEIU/mL)
- '< LLQ': All results below the LLQ cut-off value where the HBeAg result is any outcome other than 'Not Detected'
- Negative: All results below the LLQ cut-off value where the HBeAg result is 'Not Detected'

HBV DNA results reported as 'Not Detected' will be imputed as 5 IU/mL. Results reported as 'Detected' or results below the LLQ cut-off value where the status is not specified ('Detect' or 'Not Detected') will be imputed as 15 IU/mL.

The quantitative HBV RNA results will be imputed based on the HBV RNA interpretation provided by the analyzing laboratory. If the interpretation is reported as 'LLOQ' and the result is below the LLQ cut-off value, the result will be imputed as 0.825 Log10 U/mL. Interpretations

reported as 'Negative' or results below the LLQ cut-off value where the status is not specified ('LLOQ' or 'Negative') will be imputed as 0.4125 Log10 U/mL.

Screening and baseline results below LLQ will not be imputed for any of the parameters and patients with results below the LLQ value at baseline will not be included in any of the post-dose summaries or the figures for the specific parameter.

Results equal to or above the LLQ cut-off value will be analyzed as reported, except where the result has been reported as a range ('> x' or '< y') in which case the result will be imputed to one significant digit above or below the reported cut-off value (i.e., '<30' will be analyzed as 29 and '>30.0' will be analyzed as 30.1).

All results (except for HBV RNA) will be log transformed (base 10) for analysis purposes.

Imputed results will be identified in the data listings.

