### **2.2.3 Exploratory objective**

- To determine the reduction from Day 1 pre-dose baseline to post-dose nadir of HBcrAg, HBsAg, HBV DNA, HBV RNA (if scientifically feasible) and HBeAg (e+ only), in response to ARO-HBV (alone or in combination with JNJ-6379) in CHB patients as a measure of activity. The following categories will be considered for HBV DNA: >LLQ, <LLQ target detected and <LLQ target not detected.
- To evaluate the effect of single doses of ARO-HBV on cytokines (Cytokine panel A: interleukin-6 [IL-6], monocyte chemoattractant protein-1 [MCP-1], tumor necrosis factor-alpha [TNF-alpha], interleukin-8 [IL-8], interleukin-1beta [IL-1beta], interferon alpha [IFN-alpha], IL-10, IL-12 [p40], IL-12 [p70], macrophage inflammatory protein-1alpha [Mip-1alpha]) in healthy volunteers.
- To evaluate the effect of single escalating doses of ARO-HBV on complement factors Bb, CH50, C5a, C4a, and C3a in healthy volunteers.
- To collect plasma samples in healthy volunteers for subsequent metabolite identification (reported in a separate report outside of this study)
- To collect urine samples in healthy volunteers for subsequent determination of urinary excretion and metabolite identification (reported in a separate report outside of this study)
- To evaluate the effect of multiple doses of ARO-HBV (alone or in combination with JNJ-6379) on cytokines (Cytokine panel B: TNF-alpha, IFN-gamma, CXCL-9, and CXCL-10) in CHB patients
- To evaluate the effect of multiple doses of ARO-HBV (alone or in combination with JNJ-6379) on HBV patient immune cell profile including T-cells, NK cells, B cells and monocytes (if scientifically feasible)
- To evaluate the effect of multiple doses of ARO-HBV (alone or in combination with JNJ-6379) on HBV antigen specific T-cell response (if scientifically feasible).
- To evaluate the effect of interferon response gene single nucleotide polymorphisms (SNPs) including IL28B on response to ARO-HBV (alone or in combination with JNJ-6379).

- To determine the incidence and frequency of adverse events possibly or probably related to treatment as a measure of the safety and tolerability of ARO-HBV in combination with JNJ-6379 in patients chronically infected with hepatitis B virus (CHB) (Cohort 12 only).
- To determine plasma concentration of ARO-HBV, JNJ-6379, and NUCs at specified timepoints in HBV patients (Cohort 12 only).

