#### Quantitative assessments: HBV DNA, qHBsAg, qHBeAg, qHBcrAg, qHBV RNA, anti-HBsAg and ratio of bound/free anti-HBsAg (if available)

Quantitative HBV DNA, qHBsAg (overall and by IL28B genotype mutation [rs12979860 and rs8099917]), qHBeAg qHBcrAg and qHBV RNA will be logarithm (log 10) transformed, and the observed log transformed value and change from baseline of the log transformed value will be summarised descriptively for all time points assessed. In addition, for HBV DNA, qHBsAg, qHBeAg, qHBcrAg, and qHBV RNA, the change to the maximum post-dose decline (nadir) from baseline will be pooled for a nadir 'visit' and summarized by cohort as well. The nadir values will also be calculated based on the overall study period (including the follow-up visits). The ratio of bound/free anti-HBsAg will be summarized descriptively without log transformation. The change from baseline values at each post-baseline visit will also be categorized ('<0.5 log decline', '0.5-<1.5 log decline', '1.5-< 3 log decline', '> 3 log decline') and summarized. Only patients with a baseline result above the LLQ for the specific parameter will be included in the post-baseline summaries.

The summary table will also be repeated for the following subgroups (based on the categories described for the qualitative assessments below):

- Baseline HBV DNA:
  - Baseline HBV DNA Not Detected
  - Baseline HBV DNA Detected

- Baseline HBeAg:
  - Baseline qHBeAg Negative
  - Baseline qHBeAg Positive

The quantitative HBV DNA, qHBsAg, qHBeAg, qHBcrAg and qHBV RNA over time (up to Day 113) will be plotted for mean and individual subject values, based on log transformed data, by cohort. The log transformed results will be plotted on a linear scale (y-axis). The log transformed LLQ values will be added as a horizontal reference line. The change from baseline values will also be presented. The plots will also be presented for the subset of CHB patients that participated in the follow-up period and will include all available data. Only patients with a baseline result above the LLQ for the specific parameter will be included in the plots.

Qualitative assessments: HBV DNA, HBV RNA, HBsAg Loss, anti-HBsAg, HBeAg and anti-HBeAg

The quantitative HBV DNA results will be categorized as follows for the qualitative HBV DNA summary:

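### Below-limit HBV RNA is imputed by halving or quartering the log10 limit instead of the limit in U/mL, which credits 0.52 to 0.64 log of extra decline per affected result

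*SAP*

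**What the plan says.** The table under Data Handling Rules in SAP Section 11 lists a quantitation limit (LLQ), a unit and imputed values for each marker. HBV RNA is the only one whose limit is in log10 units: 1.65 log10 U/mL. If the laboratory's interpretation is 'LLOQ' and the result is below the limit, "the result will be imputed as 0.825 Log10 U/mL". The lower value, 0.4125, goes to interpretations "reported as 'Negative' or results below the LLQ cut-off value where the status is not specified".

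For HBV DNA, 'Not Detected' becomes 5 IU/mL, while "results below the LLQ cut-off value where the status is not specified ('Detect' or 'Not Detected') will be imputed as 15 IU/mL".

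The imputed values are meant for all derivations and outputs. One restriction applies: "patients with results below the LLQ value at baseline will not be included in any of the post-dose summaries" or figures for that marker. Under Quantitative assessments, change from baseline and change to nadir are summarised by cohort. "The change from baseline values at each post-baseline visit will also be categorized", with cut-points at 0.5, 1.5 and 3 log.

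On scale, the Data Handling Rules state: "All results (except for HBV RNA) will be log transformed (base 10) for analysis purposes". The Quantitative assessments text says instead that "qHBeAg qHBcrAg and qHBV RNA will be logarithm (log 10) transformed".

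**The concern.** A fraction of a logarithm is not a fraction of the quantity. Halving 1.65 sets the result at the square root of the limit in U/mL, so the answer depends on the unit chosen. If the same limit were written in kU/mL (1.65 - 3 = -1.35), halving would give -0.675 log10 kU/mL, about 211 U/mL, which is above the limit. Halving the log of the qHBsAg limit would give log10(0.05)/2 = -0.65, or 0.22 IU/mL, also above its limit. For qHBcrAg (limit 1 kU/mL, log 0) it would change nothing.

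The affected patients start with quantifiable RNA and later fall below the limit. Excluding patients who are below the limit at baseline does not remove them. Their change from baseline, nadir and decline category all contain the imputed amount, and one below-limit visit is enough to set the nadir. Cohorts with different proportions below the limit would have their mean differences stretched by the rule itself.

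Two smaller points go with this. The default for unspecified status runs in opposite directions for RNA and DNA, with no reason given. The two statements on log transformation conflict: read literally, the second would take the log of a value already in log10 units.

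**Working it through.** **Inputs**, all from the Data Handling Rules table and text: RNA limit 1.65 log10 U/mL; RNA imputed values 0.825 and 0.4125; limits and imputed values of the other markers. The category cut-points come from the Quantitative assessments text.

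**Reproducing the SAP's values.** 1.65/2 = 0.825 and 1.65/4 = 0.4125, both exact.

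**What they mean in U/mL.** Limit: 10^1.65 = 44.67. 'LLOQ': 10^0.825 = 6.68. 'Negative' or unspecified: 10^0.4125 = 2.59. The credit below the limit is -log10(fraction of the limit).

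| Marker | Limit | Imputed | Fraction of limit | Log10 credit below limit |
|---|---|---|---|---|
| qHBsAg (IU/mL) | 0.05 | 0.025 | 0.50 | 0.301 |
| qHBeAg (PEIU/mL) | 0.11 | 0.055 | 0.50 | 0.301 |
| qHBcrAg (kU/mL) | 1 | 0.5 | 0.50 | 0.301 |
| HBV DNA detected (IU/mL) | 20 | 15 | 0.75 | 0.125 |
| HBV DNA not detected (IU/mL) | 20 | 5 | 0.25 | 0.602 |
| HBV RNA 'LLOQ' (U/mL) | 44.67 | 6.68 | 0.150 | 0.825 |
| HBV RNA 'Negative' (U/mL) | 44.67 | 2.59 | 0.058 | 1.2375 |

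**Same fractions taken in U/mL**, using 1.65 + log10(f):
- Half: 1.65 - 0.301 = 1.349. Excess decline: 1.349 - 0.825 = 0.524 log.
- Quarter: 1.65 - 0.602 = 1.048. Excess decline: 1.048 - 0.4125 = 0.635 log.
- With HBV DNA's three-quarters for a detected result: 1.65 - 0.125 = 1.525. The 'LLOQ' excess would be 0.700 log.

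**Baseline needed to reach each cut-point** (imputed value plus cut-point, in log10 U/mL; the lowest quantifiable baseline is 1.65):

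| Status | Cut-point | SAP rule | Same fraction in U/mL |
|---|---|---|---|
| 'LLOQ' | 0.5 | 1.325 (always met) | 1.849 |
| 'LLOQ' | 1.5 | 2.325 | 2.849 |
| 'LLOQ' | 3 | 3.825 | 4.349 |
| 'Negative' | 0.5 | 0.9125 (always met) | 1.548 (always met) |
| 'Negative' | 1.5 | 1.9125 | 2.548 |
| 'Negative' | 3 | 3.4125 | 4.048 |

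Baselines of 2.325 to 2.849 ('LLOQ') and 1.9125 to 2.548 ('Negative') therefore move from the 0.5 to <1.5 category into 1.5 to <3. At the lower ends of those ranges the measurable fall is 2.325 - 1.65 = 0.675 log and 1.9125 - 1.65 = 0.2625 log. No imputed RNA result can fall in the <0.5 category. For HBV DNA reported as detected, that category holds for baselines under 15 × 10^0.5 = 47.4 IU/mL.

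**Unspecified status.** RNA gets 0.4125 where the 'LLOQ' value is 0.825, a further 0.4125 log of decline.

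**Scale of a cohort effect (illustration, assumed counts).** In a cohort of four with quantifiable baselines, one to four affected patients raise the mean decline by 0.524/4 = 0.13 up to 0.52 log for 'LLOQ', or 0.635/4 = 0.16 up to 0.64 log for 'Negative'.

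**The case against.** The SAP states values, not a formula, and its other markers do not share one fraction, so it can be argued that this is an odd convention and not a miscalculation. The true values are censored and the assay's limit of detection is not in the documents, so nobody can show that 1.35 and 1.05 lie nearer the truth, especially for 'Negative' results. HBV RNA is exploratory and measured only if feasible, the cohorts are descriptive, imputed results are identified in the listings, and the detected/not-detected RNA summary does not use them. An HBV DNA result that is not detected can never be in the <0.5 category either, since log10(20/5) = 0.602. All of that is correct and limits the stakes. It does not explain why one marker alone should have its logarithm divided, and flags in listings do not correct the summary tables.

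One practical objection deserves attention. Duration of response ends on return to within 20% of baseline, and the scale is not stated (SAP, Time to Event Endpoints). If the rule is applied to log10 values, an imputed 1.349 would count as returned for baselines up to 1.349/0.8 = 1.686, and 1.525 for baselines up to 1.906. The current 0.825 cannot do so (0.825/0.8 = 1.03, below the limit). With 1.35 this touches only baselines between 1.65 and 1.686, and on the natural scale it does not arise.

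**Conclusion.** The concern holds. The RNA imputation is a unit-dependent rule that departs from the way every other imputed marker in the same table is handled. It adds 0.52 log ('LLOQ') or 0.64 log ('Negative') per affected result, taking the SAP's half and quarter as fractions of the limit in U/mL. That is enough to change decline categories. The unspecified-status default adds to this in the favourable direction.

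This does not show that real RNA declines are overstated, because values below the limit are unknown. It shows that RNA is credited with more unmeasured decline than the SAP's own fractions imply. The effect on actual cohort summaries depends on how many patients fall below the limit, which the documents do not give. The primary safety analysis, the secondary HBsAg analysis and the qualitative RNA summary are unaffected. The conflict over log transformation is a matter of wording, but it should be settled in the same edit.

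**What to change.** - In the Data Handling Rules table and text, compute the RNA values in U/mL and convert: 1.35 log10 U/mL for 'LLOQ' and 1.05 for 'Negative'. The pair 1.53 and 1.05 would mirror HBV DNA, but 1.35 interacts less with the 20% duration rule.
- Give unspecified RNA status the 'LLOQ' value, matching the direction used for HBV DNA.
- In the Quantitative assessments text, remove qHBV RNA from the list to be log-transformed, or say there that it is already in log10 units.
- While editing, state the scale on which the 20% return-to-baseline rule is applied.

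The core cost is two table cells and three sentences, plus one sentence for the 20% rule, and a rerun of the RNA outputs. Reported RNA declines will become smaller where results were imputed. The final RNA tables may differ from those of the Day 113 interim analysis completed in February 2020 (SAP 17.2), which calls for a note in the clinical study report.
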